12.3. Analyses

A Statistical Analysis Plan [26] will be written and completed before the planned interim analysis and locking the Database. These specifications will detail the implementation of all the planned statistical analyses in accordance with the principal features stated in the following sections.

Patients from the Phase I part and from the Phase II part will be analyzed separately.

12.3.1. Study Conduct and Subject Disposition

Patients' disposition and reasons for ending the treatment and the study will be presented in frequency distribution tables and individual data listings. The patients not meeting the eligibility criteria, and who are considered protocol violators will be identified and described by individual data listing. Reasons for stopping treatment will be summarized as frequency

distribution in the treated patient population and, if clinically interesting, in other patient subsets. Untreated patients will be identified and described separately.

12.3.2. Baseline Characteristics and Treatment Group Comparability

Descriptive statistics of the baseline characteristics will be generated across all treated patients and, if clinically interesting, in other patient subsets. Frequency distributions will be presented for the categorical/categorized variables. Summary statistics including mean, standard deviation, median, minimum, maximum and the number of assessed patients will be calculated, as appropriate, for the quantitative variables. Individual data will be presented in listings.

The study has no comparative arm.

12.3.3. Treatment Administration/Compliance

The treatment exposure and the compliance with study treatment will be descriptively analyzed in the treated patient population and, if clinically interesting, in other patient subsets. Descriptive statistics (e.g. min, max, mean, standard deviation, and median value) will be calculated on a per-patient basis for the following variables: the number of cycles administered, the overall duration of treatment, the actual and total doses administered, and the absolute and relative dose intensity. Frequency distributions of patients and/or cycles will be used to describe dose modifications, delays and omissions, as well as the reasons for deviation from the planned therapy. Individual data will be presented in listings as reported in the relevant CRF sections.

12.3.4. Efficacy Analyses

The efficacy of NMS-01940153E will be assessed on the treated set for Phase I and evaluable set for Phase II, respectively, as defined in Section 12.2. For Phase II, only if deemed of interest and only as supportive analysis, efficacy could be also evaluated on the treated population.

12.3.4.1. Primary Efficacy Endpoint

For Phase II part, the primary efficacy endpoint ORR will be evaluated as the proportion of patients who have achieved as best overall response, CR or PR as defined by investigator-assessed RECIST 1.1. In addition to the point estimate, binomial exact confidence intervals will be provided.

The decision rules for interim analysis for futility are specified in Section [12.1](#).

12.3.4.2. Secondary Efficacy Endpoints

Objective response rate will be also calculated for Phase II part only, as the percentage of evaluable patients with best response equal to complete response (CR) or partial response (PR) as defined by investigator-assessed mRECIST. Binomial exact confidence intervals will be also provided.

Time-to-event endpoints, i.e. Duration of Response (DoR), Progression Free Survival and Overall Survival: they will be carried out on treated set for Phase I and evaluable set for Phase II, respectively. Time-to-event endpoints will be also summarized using Kaplan Meier (KM) curves and further characterized in terms of median and landmark estimates with the corresponding confidence intervals, for Phase II part only.

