- Study terminated by the Sponsor.

Data to be collected for the end of study treatment/withdrawal are described in the Schedule of Events, reported in Section [7](#).

After treatment discontinuation patients will be followed for progression, if not progressed earlier, until the start of a new anticancer therapy, and for survival. Patients will be followed for at least 28 days after the last dose of study drug for adverse events and every 2 months up to death, for secondary efficacy endpoint purpose.

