12.2. Definition of Analyzed Study Populations

The following analysis sets are defined according to ICH E9 guidelines [26].

Phase I Dose Escalation

Enrolled Set (ES): this population will include all patients who are enrolled in Phase I part, regardless of whether patients receive study treatment or not. This population will be evaluated in the analysis of patients' disposition.

Treated Set (TS): this set will include all enrolled patients who take at least one dose of NMS-01940153E. This population will be evaluated in the analysis of patients' disposition, baseline characteristics, treatment exposure, safety and efficacy.

Dose-Limiting Toxicity Evaluable Set (DLTES): this set will include all patients who receive in the first cycle at least 66% of study drug, unless the reason for non-compliance is drug-related toxicity, and undergo a DLT assessment within the DLT window. Patients not fulfilling one or more of aforementioned criteria will not be considered evaluable for MTD determination and will be substituted.

Phase II

Enrolled Set (ES): this population will include all patients enrolled in Phase II, regardless of whether patients receive study treatment or not. This population will be evaluated in the analysis of patients' disposition.

Treated Set (TS): this set will include all enrolled patients who actually receive at least one dose of NMS 01940153E. This population will be evaluated in the analysis of patients' disposition, baseline characteristics, treatment exposure and safety.

Evaluable Set (ES): this is the patient population for the primary efficacy analysis. This set will include patients of the TS who have measurable disease at baseline assessed according to RECIST 1.1 and at least one tumor evaluation on treatment, unless they die before the first tumor on-treatment assessment, in which case they will be considered treatment failure. In detail, the evaluable population for primary efficacy endpoint will consist of a subset of the evaluable population up to the total number of subjects pre-determined by the interim for futility and final analyses. This means that, if the number of evaluable subjects exceeds the planned total number of subjects at either stage, the exceeding subjects will not be considered for primary efficacy analysis. Subjects will be counted into the primary evaluable population, consecutively, based on the date of first NMS-01940153E administration.

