Evaluable Set (ES): this is the patient population for the primary efficacy analysis. This set will include patients of the TS who have measurable disease at baseline assessed according to RECIST 1.1 and at least one tumor evaluation on treatment, unless they die before the first tumor on-treatment assessment (i.e. if the patients died within 61 days from the start of the treatment considering that the first on treatment tumor assessment is foreseen at the end of cycle 2 with a time window of -2/+5 days), in which case they will be considered treatment failure. Moreover, subjects must have disease relapsed or refractory to the standard of care treatment including an immunocheckpoint inhibitor as first line and at least a tyrosine kinase inhibitor, not exceeding 3 lines of prior systemic treatment. Patients who received the RP2D defined in phase I portion as starting dose and from cycle 2 a dose increment of 25% (as per protocol version 4.0 dated 30-Jun-2022) were considered not evaluable for efficacy analysis (intra-patient dose escalation no more applicable as per protocol version 5.0). In detail, the evaluable population for primary efficacy endpoint will consist of a subset of the evaluable population up to the total number of subjects pre-determined by the interim for futility and final analyses. This means that, if the number of evaluable subjects exceeds the planned total number of subjects at either stage, the exceeding subjects will not be considered for primary efficacy analysis. Subjects will be counted into the primary evaluable population, consecutively, based on the date of first NMS-01940153E administration.

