9.7.2. Secondary Efficacy Endpoint(s)

For the Phase I part, the objective tumor response (Partial and Complete response) will be reported in patients' data listings.

Statistical Analysis Plan

ORR will be also calculated for Phase II part only, as the percentage of evaluable patients with best response equal to complete response (CR) or partial response (PR) as defined by investigator-assessed mRECIST. Binomial exact 95% confidence intervals will be also provided.

Time-to-event endpoints (i.e. DoR, PFS and OS): they will be carried out on treated set for Phase I and evaluable set for Phase II, respectively. The individual calculated times will be presented in patients' data listings together with the identification of censored vs. failure status. Time-to-event endpoints will be also summarized using Kaplan Meier (KM) curves and further characterized in terms of median, 6-month, 9-month and 12-month estimates with the corresponding 95% confidence intervals, for Phase II part only.

Reverse Kaplan-Meier method [9] will be used to estimate length of follow-up for DoR, PFS and OS by reversing censored and event observations, if applicable.

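### Phase II overall survival is analysed on the Evaluable Set, which drops treated patients who have no on-treatment scan and are alive past day 61, and this can bias OS in either direction

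*Protocol*

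**What the plan says.** Protocol 12.3.4.2 assigns the analysis sets for the time-to-event endpoints: "they will be carried out on treated set for Phase I and evaluable set for Phase II, respectively". SAP 9.7.2 repeats this and names the endpoints: "Time-to-event endpoints (i.e. DoR, PFS and OS): they will be carried out on treated set for Phase I and evaluable set for Phase II". SAP 9.7.2 also plans Kaplan-Meier medians and 6-, 9- and 12-month estimates for Phase II.

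Under Protocol 12.2, Evaluable Set members must be treated, have measurable disease at baseline, and have "at least one tumor evaluation on treatment, unless they die before the first tumor on-treatment assessment, in which case they will be considered treatment failure". SAP Section 7 puts a day limit on the early-death exception: "if the patients died within 61 days from the start of the treatment". The same section treats as not evaluable for efficacy those patients whose dose was raised from cycle 2 under protocol version 4.0.

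Survival is followed regardless of scanning. Protocol Section 10 states: "After treatment discontinuation patients will be followed for progression, if not progressed earlier, until the start of a new anticancer therapy, and for survival". The Phase II schedule (Table 4 footnotes) collects survival status every 2 months until death.

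An all-treated efficacy analysis in Phase II is optional. Protocol 12.3.4 allows it "only if deemed of interest and only as supportive analysis, efficacy could be also evaluated on the treated population", and SAP 9.7 says the same.

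**The concern.** A Kaplan-Meier curve that starts at first dose should include everyone at risk from first dose. Here, membership is settled later, and partly by the outcome itself. Of two unscanned patients, one who dies on day 60 is in the OS analysis and one who dies on day 70 is not. A scan requirement has a rationale for response rate but none for OS, and Phase I uses the Treated Set for the same endpoint.

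If patients who stop early without a scan have a poor prognosis, leaving them out raises median OS and the landmark estimates. The trial has no control arm, so readers are likely to set those estimates beside outside figures, such as the 8 to 10 months after first-line failure in Protocol 3.1. With the all-treated analysis optional, they may never see the alternative.

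**Working it through.** **The plan's own figures.** No power, event count or effect size is stated for OS, so there is no OS figure to reproduce. The sample size does reproduce. With an assumed ORR of 0.30 and an exact (Clopper-Pearson) one-sided 95% lower limit, treating 38 × 0.30 = 11.4 responders as continuous, 38 is the smallest n with a distance of at most 0.12 (distance 0.1197). Allowing for 10% non-evaluable, 38/0.9 = 42.2, rounded up to 43.

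**How many could be dropped.** With 38 evaluable patients, the enrolment cap of 40 leaves 2 (5.0%) and the inflated 43 leaves 5 (11.6%). As an upper assumption, all of these are taken as treated, unscanned and alive past day 61.

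**Day limit.** Cycle 2 ends on day 56, and 56 + 5 = 61 days. In months, t0 = 61/30.4375 = 2.004.

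**Model (assumed).** Months from first dose, with m = evaluable median and r = residual median after day 61 in the dropped patients:
- Evaluable: S_E(t) = 0.5^(t/m), with m = 8 or 10. This range is borrowed from Protocol 3.1.
- Dropped: S_D(t) = 1 up to t0, then 0.5^((t − t0)/r). The documents give no value for r, so 1 to 12 months is shown.
- All treated: S(t) = ((N − k)/N)·S_E(t) + (k/N)·S_D(t), where k of N are dropped.

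**6-month OS at r = 3.** S_D(6) = 0.5^((6 − 2.004)/3) = 0.397. The overstatement is (k/N)·(S_E(6) − S_D(6)).
- m = 8, S_E(6) = 0.595: 1.0 points at 2 of 40 and 2.3 points at 5 of 43.
- m = 10, S_E(6) = 0.660: 1.3 points at 2 of 40 and 3.1 points at 5 of 43.
- At the plan's exact 10% share: 0.10 × (0.595 − 0.397) = 2.0 points and 0.10 × (0.660 − 0.397) = 2.6 points.

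**Median OS, all treated** (solving S(t) = 0.5). Brackets show evaluable minus all-treated median in months; a positive value means the plan overstates.

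| r (months) | m = 8, 2/40 | m = 8, 5/43 | m = 10, 2/40 | m = 10, 5/43 |
|---|---|---|---|---|
| 1 | 7.43 (0.57) | 6.68 (1.32) | 9.27 (0.73) | 8.26 (1.74) |
| 3 | 7.72 (0.28) | 7.38 (0.62) | 9.52 (0.48) | 8.91 (1.09) |
| 6 | 8.00 (0.00) | 8.00 (0.00) | 9.85 (0.15) | 9.67 (0.33) |
| 8 | 8.11 (−0.11) | 8.25 (−0.25) | 10.00 (0.00) | 10.00 (0.00) |
| 12 | 8.24 (−0.24) | 8.57 (−0.57) | 10.19 (−0.19) | 10.44 (−0.44) |

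The break-even is r = m − t0: 8 − 2.004 = 5.996 and 10 − 2.004 = 7.996 months.

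**Survival at day 61.** Everyone dropped is alive then, so the Evaluable Set understates it. For m = 8 it gives 0.841, against 0.849 (2 of 40) or 0.859 (5 of 43) in all treated. For m = 10 the figures are 0.870 against 0.877 or 0.885.

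**The case against.** **Early deaths are kept.** This stands, and it limits the size. A reader might model the dropped patients as exponential from first dose. With a 3-month median, that has 1 − 0.5^(2.004/3) = 37% of them dying by day 61, and the SAP keeps exactly those deaths. The model above therefore conditions on being alive at day 61.

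**Few patients should be unscanned.** Protocol 11.3.1 plans imaging at clinical deterioration and at the end of the last cycle. This shrinks the group but does not empty it. The end-of-treatment scan is waived if one was done in the previous 4 weeks, and the baseline scan may be up to 28 days old at treatment start, so a very early stopper may have no scan due. The plan itself allows for 10% non-evaluable.

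**Some of those dropped cannot be followed.** This also stands. Under Protocol Section 10, nothing more is collected once consent to further information is withdrawn. For these patients, and for those lost to follow-up, the Treated Set mainly adds censored time. It is not true in general that an observed death is discarded.

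**PFS is different.** A reader might infer that PFS is inflated in the same way. The documents do not support that. Its progression component is RECIST 1.1, and the censoring rules are in a separate appendix that was not available. If unscanned patients are censored at day 1, adding them leaves the PFS curve unchanged. Off-treatment scans every 2 months could still show a genuine progression in a patient without an on-treatment scan, so the effect is unknown.

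**OS is descriptive and partly covered elsewhere.** The plan has no OS test and no OS benchmark; its only benchmark is the 18% ORR. The 8 to 10 months follow first-line failure, whereas the sample-size rationale describes third line. Deaths are tabulated on the treated population (SAP 9.8.3), and patients excluded from efficacy are listed (SAP 9.2). All of this lowers the stakes, but none of it supplies an all-treated OS curve.

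**Conclusion.** The point holds for OS. Evaluable Set membership depends on a later scan or an early death, so it is the wrong main set for an endpoint timed from first dose that needs no scan.

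The bias is possible but its direction is not established. With a 3-month residual median in those dropped, median OS is overstated by about 0.3 to 1.1 months and 6-month OS by about 1.0 to 3.1 points. For the median, the bias is about zero at a residual median of 6 to 8 months and reverses above that. These figures rest on exponential survival, evaluable medians taken from background text, every non-evaluable patient being an unscanned survivor past day 61, and an assumed residual median. Scans at deterioration would make the affected group smaller.

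A reader might conclude that the plan inflates both OS and PFS. That goes too far: the sign for OS depends on survival after day 61, which the documents do not give, and no PFS magnitude can be claimed. DoR is unaffected because responders have scans.

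**What to change.** In Protocol 12.3.4.2 and SAP 9.7.2:
- Make the Treated Set (all patients with at least one dose, timed from first dose) the main set for Phase II OS. Keep the Evaluable Set version as supportive.
- Report Phase II PFS on the Treated Set as well, under the appendix censoring rules. Its result may not change.
- Keep DoR on responders.
- State how the patients dose-escalated under protocol version 4.0 are handled. The Treated Set brings them back and mixes regimens. One option is to include them and add a sensitivity analysis that leaves them out.
- Adjust Protocol 12.3.4 and SAP 9.7 so that the all-treated OS analysis is no longer optional.

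No new data are needed, because survival status is already collected. The cost is revised wording in both documents and a little extra analysis. OS may look slightly less favourable.

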12.3.5. Outcomes Research Analyses

Not applicable

12.3.6. Safety Analyses

Unless otherwise specified, the safety analyses will be performed on the treated set by assigned dose level and overall for Phase I and overall for Phase II.

Adverse events will be coded by Medical Dictionary for Regulatory Activities (MedDRA) and their severity will be graded according to the NCI Common Terminology Criteria for Adverse Events (CTCAE, version 5.0). The analysis will focus on the events reported after the start of treatment (treatment emergent adverse events). For each dose level and overall, the incidence of AEs will be grouped by System Organ Class (SOC) and by preferred term. Each patient will be counted once according to the worst grade reported throughout the whole treatment period for each SOC and/or for each preferred term. If clinically indicated, selected AEs will be presented by treatment cycle (Cycle 1 vs. Cycles >1). In addition, SAEs, AEs with severity grade 3-5, AEs leading to treatment withdrawal and AEs related to study treatment, will be reported separately.

The DLT occurrence during the first treatment cycle will be reported for the Dose-Limiting Toxicity Evaluable Set (DLTES).

Frequency of deaths will be presented overall and by dose level, by relationship to the study treatment and according to the time since treatment discontinuation.

Laboratory data will be graded according to the NCI CTCAE scale (version 5.0) whenever possible. Laboratory abnormalities will be summarized in frequency distribution tables by dose level and treatment period (i.e. treatment Cycle 1, Cycle >1 and the whole treatment period). For each parameter, patients will be classified based on the maximal severity grade observed during the analyzed time-window. Changes of severity grade vs. baseline will be evaluated by shift tables. Selected laboratory parameters will be further explored by analyzing the nadir/zenith values, the time to nadir/zenith and the time to recovery after nadir/zenith, as clinically indicated.

For the laboratory data not graded by the NCI CTCAE scale, a cross tabulation of on treatment worst finding versus baseline finding will be presented reporting the number of patients with values within or out of the normal range.

All collected safety data (including vital signs, ECG, laboratory assessments and adverse events, etc.) will be presented in individual patients' data listings. Identification of clinically relevant values and calculation of changes from baseline will be provided for those parameters and conditions deemed of clinical relevance.

12.3.7. Analyses of Other Endpoints

12.3.7.1. Alpha-Fetoprotein as Surrogate Marker of Efficacy

Exploratory analysis on the relationship between AFP levels and treatment efficacy variables in patients treated with NMS-01940153E will be performed if sufficient data are collected.

12.3.7.2. Pharmacokinetic

12.3.7.2.1. Phase I Dose Escalation

The pharmacokinetics of NMS-01940153E and its metabolite NMS-03593478 in plasma and urine will be assessed by standard non-compartmental analysis using Phoenix WinNonlin 8.1 or later version (Certara Company).

The following pharmacokinetic parameters will be provided on both Day 1 and Day 15: maximum concentration (C_{max}) and related time of achievement (T_{max}), last detectable concentration (C_{last}) and related time of observation (T_{last}), area under concentration versus time up to 168 hours (dosing interval), half-life of the terminal phase ($t_{1/2,z}$), plasma clearance (CL), volume of distribution (Vss) and renal clearance (CLR).

On Day 1, for NMS-01940153E and NMS-03593478, maximum concentration, $C_{max,D1}$, and related time of achievement, $T_{max,D1}$, last detectable concentration, $C_{last,D1}$, and related time of observation, $T_{last,D1}$, will be taken directly from the raw data.

Area under concentration versus time up to the last detectable concentration (AUClast) will be calculated using the linear trapezoidal rule. The half-life of the terminal phase, $t_{1/2,z}$, will be determined by linear regression analysis of the natural-log concentration versus time curve according to the formula:

$$t_{1/2,z} = \frac{\ln(2)}{\lambda_z}$$

where λ_z is the slope of the regression line. A minimum of three data points will be used in calculating λ_z .

$AUC_{\infty}(D1)$ will be calculated by adding the portion of the area calculated as $C_{last,D1}/\lambda_z$ to AUClast,D1.

The clearance (CL) of NMS-01940153E will be calculated according to the formula:

$$CL = \frac{\text{Dose}}{\text{AUC}_{\infty_{D1}}}$$

The volume of distribution at steady state (V_{ss}) of NMS-01940153E will be calculated according to the formula:

$$V_{ss} = CL \cdot MRT, \text{ where } MRT = \frac{AUMC_{D1}}{AUC_{D1}} - \frac{t_{inf}}{2}$$

On Day 15, C_{max,D15}, T_{max,D15}, Clast,D15 and Tlast,D15 will be taken directly from the raw data.

AUC_{0-168,D15}, AUClast,D15 and AUCD15 will be calculated as on Day 1.

The clearance (CL) of NMS-01940153E will be calculated according to the formula:

$$CL = \frac{\text{Dose}}{\text{AUC}_{\tau, D15}}$$

where AUC τ is the area under the curve in the dosing interval.

Accumulation ratios for NMS-01940153E and NMS-03593478, based on C_{max} (R_A, C_{max}) and AUC_{last} (R_A, AUC_{last}) will be calculated as the ratio between the individual parameter obtained on Day 15 to the corresponding one on Day 1.

On Day 1 and Day 15, metabolite to parent ratio will be calculated based on C_{max} and AUC_{last} values.

On Day 1 and Day 15, the amount of NMS-01940153E and its metabolite NMS-03593478 excreted in urine in the time interval 0-72 h (Ae₀₋₇₂) will be calculated multiplying the urinary concentration by the urinary volume in the collection times: 0-6, 6-24, 24-48 and 48-72 hours. The parameter will be also expressed as percent of dose (fe%). For the metabolite, the parameter expressed as percent of dose will be calculated after correction of the dose for the molecular weight of the compound.

Renal clearance of NMS-01940153E and its metabolite NMS-03593478 will be calculated as:

$$CLR = Ae_{0-72} / \text{AUC}_{0-72}$$

Statistical analysis

Descriptive statistics (mean \pm SD, CV%, min, max, median) will be calculated for plasma and urine concentration data and pharmacokinetic parameters.

Statistical analysis will be performed after a log-transformation of the data of NMS-01940153E treatment. For each group separately, a mixed effect model will be fitted with day

as fixed effect and subject as a random effect. Day 15 will be compared to Day 1 for each dose level. The ratio will be calculated by back-transforming the difference between the Least Square means. Using the estimate of variance, 90 % confidence intervals will be calculated for the difference and back-transformed. Results of the analyses will be reported in the paragraph of the statistical results.

The power method will be used to evaluate the dose proportionality of NMS-01940153E and possibly its metabolite. C_{\max} , AUC_{last} , AUC_{0-168} and AUC data on Day 1 and Day 15. Dose *versus* C_{\max} and AUC s relationship will be performed using the power model

$$y = a \cdot \text{Dose}^b$$

This relationship becomes linear after a logarithmic transformation

$$\log(y) = \log(a) + b \cdot \log(\text{dose})$$

where a is the intercept to y (AUC) axis and b is the slope of the regression line. Dose proportionality required slope to be close to unity for dose dependent parameters, and decision on dose proportionality will be made based on the inclusion of the theoretical slope of 1 in the 90 % confidence intervals.

